9.5.4 Pregnancy Reporting

Details of all pregnancies in female subjects will be collected after the start of study drug as per SoA ([Table 1](#)).

- If a pregnancy is reported, the Investigator will record pregnancy information on the appropriate form (pregnancy form) and submit it to the Sponsor within 24 hours of learning of the female subject pregnancy.
- While pregnancy itself is not considered to be an AE or SAE, any pregnancy complication or elective termination of a pregnancy for medical reasons will be reported as an AE or SAE.
- Abnormal pregnancy outcomes (e.g., spontaneous abortion, fetal death, stillbirth, congenital anomalies, ectopic pregnancy) are considered SAEs and will be reported as such.
- The subject will be followed to determine the outcome of the pregnancy. The Investigator will collect follow-up information on the subject and the neonate up to one month post-partum, and the information will be forwarded to the Sponsor.
- Any post study pregnancy-related SAE considered reasonably related to the study drug by the Investigator will be reported to the Sponsor. While the Investigator is not obligated to actively seek this information in former (study subjects) beyond the resolution of the pregnancy, he or she may learn of an SAE through spontaneous reporting.

Should a female subject become pregnant during the course of the study after dosing, she will continue to be followed for safety and pregnancy outcomes. Subjects who have a positive pregnancy test at Day 1, prior to randomization, will be considered screen failures.

If a subject is found pregnant post study drug administration, the subject will only be monitored for safety.

9.5.5 Death Events

Events resulting in death will be an SAE regardless of association to study drug. Death is an outcome and should not be reported as an event term. The event that leads to the death should be reported as the SAE term.

10. SAFETY OVERSIGHT

10.1. Internal Sponsor Review

Safety data will be monitored on an ongoing basis by the Investigator (or medically qualified designee) and the Sponsor's Medical Monitor (or designee) in order to promptly identify and flag any event that potentially contributes to a Stopping Rule.

The lead Medical Monitor will be a physician experienced in the conduct of research clinical studies whose primary responsibility will be to monitor subject safety. The Medical Monitor will be responsible for reviewing the cumulative safety data, including a review of safety laboratory test results and adverse event reporting. The Medical Monitor will be familiar with study-specific data as well as relevant background information about the disease, investigational drug, and target population under study. The Medical Monitor(s) will be empowered to request a SMC safety review which can suspend the study, recommend amendments to the protocol, and/or to request further information.

10.2. Safety Monitoring Committee

A Safety Monitoring Committee (SMC) will be created to provide oversight of the conduct of the trial to ensure the safety of subjects. The committee will consist of independent physicians and/or scientists with vaccine clinical trials experience or expertise, and the Medical Monitor, who does not enroll subjects into the study.

The SMC will be assigned by the Sponsor prior to the beginning of the study and will provide oversight of the study throughout the duration of the study period (Day 1 through Day 365) as needed. Ad hoc meetings will be convened if any predefined stopping rules are met, or any serious vaccine-related events or trends are observed.

The SMC will function in accordance with the following provisions: (1) United States (US) Code of Federal Regulations (CFR) applicable to clinical studies (21 CFR Part 50, 21 CFR Part 54, 21 CFR Part 312.55 and 312.56. (2) ICH E6 and 62 Federal Register 25691 (1997): Good Clinical Practice (GCP) Consolidated Guideline.

Further details regarding data safety monitoring guidelines will be included in the SMC Charter, which is the governing document that supersedes this section of the protocol.

11. STATISTICAL CONSIDERATION

A formal Statistical Analysis Plan (SAP) will be developed and finalized prior to locking the database. The full details of data presentation and analyses will be provided in SAP.

Additional statistical analyses other than these described in this section may be performed if deemed appropriate and included in the SAP. Any deviations from the final SAP or from what is outlined in the protocol will be discussed in the final study report (CSR).

11.1 Sample Size Determination

A sample size of 76 randomized subjects (30 each in medium and high dose levels and 16 in placebo) is not based on formal statistical testing but rather based on clinical judgement and predicted to yield meaningful safety and immunogenicity results. Placebo was added for safety comparison.

11.2 Multiplicity Adjustment

No multiplicity adjustment will be implemented for this study.

11.3 Population for Analysis

For purposes of analysis, the following analysis sets are defined:

Table 8: Populations for Analyses

Analysis Population	Description
Screened	All subjects who enter screening (assigned a screening number)
Intent to Treat (ITT)	All subjects who are randomized. The analyses using ITT will be based upon the randomization group allocated.
Per Protocol	All subjects in the ITT set who receive one dose and who have not violated any inclusion/exclusion criteria and / or deviated in a way that could influence their Immunogenicity assessments.
Safety	All randomized subjects who receive at least 1 dose of the study drug. Subjects will be analyzed according to the treatment (vaccine) they actually received. All safety analyses will be conducted based on the Safety set.
Immunogenicity	All randomized subjects who receive at least 1 dose of the study drug and have at least one valid immunogenicity result after Day 1. Subjects will be analyzed according to the treatment (vaccine) they actually received. All immunogenicity analyses will be conducted based on the Immunogenicity set.

11.4 Statistical Analysis Plan

11.4.1 General Approach

The SAP will be developed and finalized before database lock and breaking the blind for any of the planned analyses. It will describe the subject sets to be included in the analyses and the procedures for accounting for missing, unused, and spurious data. This section provides a summary of the planned statistical analyses of the primary endpoints.

11.4.2 Analysis of the Primary and Secondary Safety End Points

Safety will be summarized for the safety set (active vs. placebo). Solicited Symptoms of Reactogenicity, unsolicited AEs, SAEs, physical examination, and vital signs will be summarized descriptively by treatment group and study visit.

Analyses will be performed for the total set (active vs. placebo). All results will be presented descriptively and summarized by treatment groups.

Endpoint	Statistical Analysis Methods
Primary (measured from Day 1 through Day 29)	
Frequency, duration, and severity of Solicited Symptoms of Reactogenicity (local, systemic) measured daily for 1 week following vaccination.
 
Frequency, duration, and severity of unsolicited AEs, and SAEs through the active period (4 weeks post dose).
 
Descriptive statistics will be provided for each reactogenicity endpoint for each dose. Local reactions and systemic events from Day 1 through Day 8 after each dose will be presented by severity and cumulatively across severity levels. Descriptive summary statistics will include counts and percentages of subjects with the indicated endpoint and the associated Clopper-Pearson 95% CIs.
 
AEs will be categorized according to the Medical Dictionary for Regulatory Activities (MedDRA[®]) terms. Descriptive summary statistics (counts, percentages, and associated Clopper-Pearson 95% CIs) will be provided for any TEAEs for each vaccine group as well as the placebo group. SAEs will be categorized according to MedDRA[®] terms. The safety analyses are based on the safety set. Subjects will be summarized by vaccine group and placebo according to the study drug they actually received. Missing reactogenicity Diary data will not be imputed; missing TEAE dates will be handled according to the rules determined in the SAP.

Secondary (measured through Day 365)	Frequency, duration, and severity of SAEs, AESIs and NOCIs for 1 year following the study drug dose.

11.4.3 Analysis of Primary, Secondary, and Exploratory Immunogenicity and Endpoints

Immunogenicity will be summarized according to the treatment group to which the subject was randomized.

Immunogenicity samples will be drawn for all subjects. Immunogenicity analyses will be based upon results from appropriately sized subsets of samples, according to the purpose. The statistical analysis of immunogenicity results will be primarily based on the evaluable immunogenicity sets.

An additional analysis will be performed based on the all-available sets if there is a large enough difference in sample size between the all-available immunogenicity set and the evaluable immunogenicity set.

Immunogenicity will be summarized by the total set (active vs. placebo). For all endpoints, all measures will be analyzed comparing the two active vaccine groups. The immunogenicity set will be used for this analysis. All results will be presented descriptively and summarized by treatment groups.

Endpoint	Statistical Analysis Methods
Primary (Key Immunogenicity Endpoints measured from Day 1 through Day 29)	Serum and breastmilk VP1 specific IgA for both GI.1 and GII.4 by Meso Scale Discovery will be summarized descriptively through the active period (4 weeks post dose).
Secondary (measured through Day 180)	Serum VP1 specific IgA and IgG for both GI.1 and GII.4 by Meso Scale Discovery will be summarized descriptively through 6 months post dose. Serum Blocking titers 50 (BT50) (GI.1 and GII.4) by Histo-blood group antigen (HBGA) assay will be summarized descriptively through 6 months post dose. Breastmilk VP1 specific IgA for both GI.1 and GII.4 by Meso Scale Discovery will be summarized descriptively through 6 months post dose.
Exploratory	For specific exploratory immunogenicity endpoints please refer to Section 8.2-Immunogenicity Assessments- Exploratory Immunogenicity Assessments.

11.4.4 Baseline Descriptive Statistics

Demographic data, baseline characteristics, physical examination, concomitant medications, medical history data and study medication exposure will be summarized by treatment group.

11.4.5 Tabulation of Individual Subject Data

By subjects listing will be produced for each variable by treatment group and study visit.

12. ETHICAL CONSIDERATIONS

12.1 Ethical Conduct of the Study

The study will be conducted in accordance with the protocol, legal and regulatory requirements, and the general principles set forth in the International Ethical Guidelines for Biomedical Research Involving Human Subjects (Council for International Organizations of Medical Sciences [CIOMS] 2002), ICH Guideline for Good Clinical Practice, and the Declaration of Helsinki.

12.2 Institutional Review Board

It is the responsibility of the Investigator to have prospective approval of the study protocol, protocol amendments, informed consent documents, and other relevant documents, e.g., recruitment advertisements, if applicable, from the IRB/IEC. All correspondence with the IRB/EC should be retained in the Investigator file.

The only circumstance in which an amendment may be initiated prior to IRB/IEC approval is where the change is necessary to eliminate apparent immediate hazards to the subjects. In that event, the Investigator must notify the IRB/IEC and Sponsor in writing immediately after the implementation.

They should also be informed of any event likely to affect the safety of the subjects or the continued conduct of the clinical study, in particular any change in safety. All updates to the IB will be sent to the IRB/IEC and to Health Authorities (Competent Regulatory Authority), as required by local regulation. A progress report is sent to the IRB/IEC at least annually and a summary of the study's outcome at the end of the clinical study.

12.3 Informed Consent Process

Informed consent is a process that is initiated prior to the individual's agreeing to participate in the study and continues throughout the individual's study participation. Consent forms will be Institutional Review Board (IRB)-approved and the subject will be asked to read and review the document. The Investigator will explain the research study to the subject and answer any questions that may arise. A verbal explanation will be provided in terms suited to the subject's comprehension of the purposes, procedures, and potential risks of the study and of their rights as research subjects. Subjects will have the opportunity to carefully review the written consent form and ask questions prior to signing.

The subjects should have the opportunity to discuss the study with their family or surrogates or think about it prior to agreeing to participate. The subject will sign the informed consent documents for herself and her infant prior to any procedures being done specifically for the study. Subjects must be informed that participation is voluntary and that they may withdraw from the study at any time, without prejudice. A copy of the informed consent document will be given to the subjects for their records. The informed consent process will be conducted and documented in the source document (including the date), and the forms signed, before the subject undergoes any study-specific procedures. The rights and welfare of the subjects will be protected by emphasizing to

them that the quality of their medical care will not be adversely affected if they decline to participate in this study.

If the trial is involving vulnerable population, video recording of entire informed consent process should be ensured depending on the norms of respective country's regulatory authorities.

12.4 Insurance Compensation

The Sponsor certifies that it has taken out a liability insurance policy covering all clinical trials under its sponsorship. This insurance policy is in accordance with local laws and requirements. The insurance of the Sponsor does not relieve the Investigator and the collaborators from any obligation to maintain their own liability insurance policy. An insurance certificate will be provided to the IRB/IEC or regulatory authorities in countries requiring this document.

12.5 Stipends/Rewards/Compensation for Participation

Subjects may be provided with a stipend according to local practice to compensate for the time and travel required for study visits and procedures. Participating subjects will be given a manual breast pump set.

12.6 Subject Confidentiality

Subject confidentiality and privacy will be strictly held in trust by the participating Investigators, their staff, and the Sponsor and their interventions. This confidentiality is extended to cover testing of biological samples in addition to the clinical information relating to subjects. Therefore, the study protocol, documentation, data, and all other information generated will be held in strict confidence. No information concerning the study, or the data will be released to any unauthorized third party without prior written approval of the Sponsor. All research activities will be conducted in as private a setting as possible.

The study monitor, other authorized representatives of the Sponsor, representatives of the Institutional Review Board (IRB), regulatory agencies or pharmaceutical company supplying study product may inspect all documents and records required to be maintained by the investigator, including but not limited to, medical records (office, clinic, or hospital) and pharmacy records for the Subjects in this study. The clinical study site will permit access to such records.

The study subject's contact information will be securely stored at each clinical site for internal use during the study. At the end of the study, all records will continue to be kept in a secure location for as long a period as dictated by the reviewing IRB, Institutional policies, or Sponsor requirements.

Study subject research data, which is for purposes of statistical analysis and scientific reporting, will be transmitted to and stored at sponsors designated vendor. This will not include the subject's contact or identifying information. Rather, individual Subjects and their research data will be identified by a unique study identification number. The study data entry and study management systems used by clinical sites and by designated vendor research staff will be secured and password protected. At the end of the study, all study databases will be de-identified and archived.

12.7 Reporting of Safety Issues and Serious Breaches of the Protocol or ICH GCP

In the event of any prohibition or restriction imposed (i.e., clinical hold) by an applicable regulatory authority in any area of the world, or if the Investigator is aware of any new information that might influence the evaluation of the benefits and risks of the investigational product, Sponsor should be informed immediately.

In addition, the Investigator will inform Sponsor immediately of any urgent safety measures taken by the Investigator to protect the study subjects against any immediate hazard, and of any serious breaches of this protocol or of ICH GCP that the Investigator becomes aware of.

13. DATA HANDLING AND RECORD KEEPING

13.1 Source Documents

Source data are all information, original records of clinical findings, observations, or other activities in a clinical trial necessary for validation of the clinical data. Examples of these original documents and data records include, but are not limited to, hospital records, clinical and office charts, laboratory notes, memoranda, subjects' memory aid or evaluation checklists, pharmacy dispensing records, recorded data from automated instruments, copies or transcriptions certified after verification as being accurate and complete, microfiches, photographic negatives, microfilm or magnetic media, x-rays, and subject files and records kept at the pharmacy, at the laboratories, and medico-technical departments involved in the clinical trial. All information on the CRF will be traceable to these source documents, which are generally maintained in the subject's study file.

The source documents will include a copy of the signed Informed Consent/ Health Insurance Portability and Accountability Act (HIPAA) authorization. The source document data collection forms for screening, Outpatient visits and AEs will also serve as CRF data collection instruments.

The Investigator is responsible for ensuring the accuracy, completeness, legibility, and timeliness of the data reported. Source documents are maintained for recording data for each subject enrolled in this clinical trial. Study subjects' data collected on the CRF during the trial will only be identified by subject number. If, as an exception, it is necessary for safety or regulatory reasons to identify the subject, both the Sponsor and the Investigator are bound to keep this information confidential.

13.2 Case Report Forms (CRF)

As used in this protocol, the term CRF should be understood to refer to either a paper form or an electronic data record or both, depending on the data collection method used in this trial.

A CRF is required and should be completed for each included subject. The completed original CRFs are the sole property of Vaxart and should not be made available in any form to third parties, except for authorized representatives of Vaxart or appropriate regulatory authorities, without written permission from Vaxart.

The Investigator has ultimate responsibility for the collection and reporting of all clinical, safety, and laboratory data entered on the CRFs and any other data collection forms (source documents)

and ensuring that they are accurate, authentic/original, attributable, complete, consistent, legible, timely (contemporaneous), enduring, and available when required.

The CRFs must be signed by the Investigator or by an authorized staff member to attest that the data contained on the CRFs are true. Any corrections to entries made in the CRFs or source documents must be dated, initialed, and explained (if necessary) and should not obscure the original entry.

13.3 Data Collection and Management Responsibility

Data collection is the responsibility of the clinical trial staff at the site under the supervision of the site Investigator. The Investigator is responsible for ensuring the accuracy, completeness, legibility, and timeliness of the data reported.

All source documents should be completed in a neat, legible manner to ensure accurate interpretation of data. Hardcopies of the study visit worksheets will be provided for use as source document worksheets for recording data for each subject enrolled in the study.

Data recorded in the eCRF/CRF derived from source documents should be consistent with the data recorded on the source documents.

Clinical data (including AEs, concomitant medications, and expected adverse reactions data) and clinical laboratory data will be entered into a data capture system that is 21 CFR Part 11-compliant. The data system includes password protection and internal quality checks, such as automatic range checks, to identify data that appear inconsistent, incomplete, or inaccurate. Clinical data will be entered directly from the source documents.

13.4 Record Retention

Study documents should be retained for a minimum of 10 years after the last approval of a marketing application in an International Conference on Harmonisation (ICH) region and until there are no pending or contemplated marketing applications in an ICH region or until at least 10 years have elapsed since the formal discontinuation of clinical development of the study drug.

These documents should be retained for a longer period, however, if required by local regulations. No records will be destroyed without the written consent of the Sponsor, if applicable. It is the responsibility of the Sponsor to inform the Investigator when these documents no longer need to be retained.

13.5 Property Rights and Data Protection

Subjects will be assigned a unique identifier by the Sponsor. Any subject records or datasets that are transferred to the Sponsor will contain the identifier only; subject names or any information which would make the subject identifiable will not be transferred.

The subject must be informed that their personal study-related data will be used by the Sponsor in accordance with local data protection law. The level of disclosure must also be explained to the

subject who will be required to give consent for their data to be used as described in the informed consent.

The subject must be informed that their medical records may be examined by clinical quality assurance auditors or other authorized personnel appointed by the Sponsor, by appropriate IRB/IEC members, and by inspectors from regulatory authorities.

All information, data and documents including results and investigational products provided by the Sponsor or its designee are and remain the sole property of the Sponsor.

The Sponsor may use or exploit all the results at its own discretion.

14. QUALITY CONTROL AND QUALITY ASSURANCE

14.1 Early Safety Data Review AND/OR Committee

Subject safety will be continuously monitored by the Sponsor or designee, which includes safety signal detection during the study.

All safety data collected will be summarized and reviewed by the sponsor's internal/external safety monitoring committee for agreement of next steps.

In particular, data will be reviewed by the sponsor for identification of the following events that would potentially contribute to a requirement to [pause/stop] the study.

- One or more subjects experiences a treatment-related serious adverse event (SAE) of any grade
- Two or more subjects experience the same treatment-related grade ≥ 3 solicited symptom within one week following vaccination.
- Two or more subjects experience the same treatment-related unsolicited grade "severe" AE between Day 1 and Day 29 (Active Period).

Enrollment will be paused during the review. If a pausing/stopping rule is met, a decision will be made, based on the review, as to whether enrollment in the study will be allowed to resume. If no dose-related toxicities are observed, and upon the recommendation of the SMC following review of safety data, enrollment of the remaining subjects will be initiated.

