9.4 Monitoring and Follow-up of AEs, NOCIs, and SUSARs during Trial

9.4.1 Monitoring and Follow-up of SAEs from Day 1 to Day 29 after Vaccination

Following AEs/SAEs, could appear during the entire course of the trial after vaccination. The following symptoms will be captured via Solicited Symptoms during Day 1 to Day 8. After Day 8 they will be captured as unsolicited adverse events. SAEs are captured from the first dose of study product.

- Fever/pyrexia
- Diarrhea
- Nausea
- Vomiting
- Abdominal pain
- Malaise/fatigue
- Anorexia
- Headache
- Myalgia (muscle pain)

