#### 13.1 Solicited Symptoms of Reactogenicity

Solicited symptoms are predefined signs and symptoms of reactogenicity for which the subject is specifically questioned, and which are noted by the subject in their Solicited Symptom Diary, including:

- Fever (any temperature 100.4°F or higher)
- Headache
- Myalgia (muscle pain)
- Abdominal Pain
- Anorexia (defined and not eating)
- Nausea
- Vomiting
- Diarrhoea
- Malaise/Fatigue

Subjects will utilize a Solicited Symptom Diary issued on the day of the vaccination to record solicited symptom daily for one week (from Day 1 to Day 8) following that administration. After Day 8 solicited symptoms will be captured as unsolicited Adverse Events as described in [section 13.2](#) with Day 8 as date of onset.

The count and percentage of subjects and the associated Clopper-Pearson 95% CIs reporting at least one solicited symptom during 8 days after vaccine administration (the 8 days include Day 1) will be summarized for each dose and presented by severity and cumulatively across severity levels as listed below:

- Grade 1 Solicited Symptoms
- Grade 2 Solicited Symptoms
- Grade 3 Solicited Symptoms
- Grade 4 Solicited Symptoms

where Grade 1 is mild, Grade 2 is moderate, Grade 3 is Severe, and Grade 4 is Potentially Life threatening as defined in Table 10 “Grading of Solicited Symptoms of Reactogenicity”.

Missing reactogenicity Diary data will not be imputed.

All the solicited symptoms collected during the active period of the study will also be presented for each treatment arm, study day, by severity in by-subject listing.

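### Low priority: the two-subject criteria in Protocol 14.1 count the same diary symptom separately before and after Day 8, so one early and one late severe related case meet neither

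*Protocol*

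**What the plan says.** Protocol 14.1 lists three kinds of event that could contribute to pausing or stopping:

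1. One or more women with a related serious adverse event.
2. Two or more women with the same related Grade 3 or higher "solicited symptom within one week following vaccination".
3. Two or more women with the same related severe unsolicited "AE between Day 1 and Day 29 (Active Period").

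It adds: "Enrollment will be paused during the review".

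Protocol 9.4.1 names nine symptoms (fever, diarrhea, nausea, vomiting, abdominal pain, malaise/fatigue, anorexia, headache, myalgia) that are solicited from Day 1 to Day 8. Then: "After Day 8 they will be captured as unsolicited adverse events". SAP 13.1 agrees ("After Day 8 solicited symptoms will be captured as unsolicited Adverse Events") and gives a symptom carried over in this way a Day 8 onset. Under Protocol 9.1, an event that fits the prelisted diagnosis and onset window is not unsolicited, so a first-week diary symptom does not enter the third tally.

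Around these counts, Protocol 10.1 asks the investigator and the Medical Monitor to "promptly identify and flag any event that potentially contributes to a Stopping Rule" and lets the Medical Monitor request an SMC review. Protocol 10.2 states: "Ad hoc meetings will be convened if any predefined stopping rules are met". It extends this to serious vaccine-related events and to trends, and it defers detail: "Further details regarding data safety monitoring guidelines will be included in the SMC Charter".

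**The concern.** Criteria 2 and 3 use the same threshold of two women and, for these nine symptoms, concern the same clinical event. They differ only in how the event was captured, by diary or on the adverse event page. Criterion 3 runs to Day 29, so the plan already treats a related severe symptom after the first week as relevant to a pause. Nothing supplied explains why two women on the same side of Day 8 should count and two women on opposite sides should not.

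What is at stake is modest. In the split pattern, no count prompts the review during which enrolment is held, and more women may be dosed before someone acts on judgement. Each woman receives a single dose and the stated action is an enrolment pause, so the point has value only while enrolment is open. No endpoint, estimate or analysis is affected.

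**Working it through.** **Logic.** Let e be the number of women with a related, non-serious, severe case of one symptom that starts and resolves by Day 8. Let l be the number whose case starts after Day 8. As written, a criterion is met if e ≥ 2 or l ≥ 2. With one tally it is met if e + l ≥ 2. The two rules differ in one cell only, e = 1 and l = 1. Example: one woman has severe vomiting on Day 3 that resolves, and another has severe vomiting from Day 12. The solicited count is 1, the unsolicited count is 1 and the serious count is 0.

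**Two features narrow the cell.** A related serious case meets criterion 1 alone. An early case that continues past Day 8 is re-recorded as unsolicited, so if it is still severe it may count alongside the late case under criterion 3.

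**Size.** The plan states no operating characteristics for these criteria, so there is no figure to reproduce. The 60 vaccinees (30 + 30) come from Protocol 11.1. Everything else is assumed: q is the chance per woman of a related severe case of one given symptom, and p is the share of such cases with early onset. Related events on placebo are not modelled.

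Ignoring enrolment:

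- One tally: 1 − (1−q)^60 − 60q(1−q)^59
- Gap: 60 × 59 × (qp) × (q(1−p)) × (1−q)^58

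At q = 2% and p = 80%, the gap is 3540 × 0.016 × 0.004 × 0.98^58 = 0.2266 × 0.3098 = 7.0 points (26.8% as written, 33.8% with one tally). Over other values, in points:

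| q | p = 80% | p = 90% | p = 95% | p = 99% |
|---|---|---|---|---|
| 0.5% | 1.06 | 0.60 | 0.31 | 0.07 |
| 1% | 3.16 | 1.78 | 0.94 | 0.20 |
| 2% | 7.02 | 3.95 | 2.08 | 0.43 |
| 3% | 8.71 | 4.90 | 2.59 | 0.54 |

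If a share s of cases is serious and a share r of early cases persists as severe past Day 8, the gap is multiplied by (1−s)²(1−r). With s = r = 20%, 7.02 × 0.64 × 0.80 = 3.59.

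**While enrolment is open.** This is a simulation of 300,000 trials per cell. Dosing is uniform over T days, early onset uniform over 0–7 days after dosing and late onset uniform over 8–28 days. A criterion counts only if met by T. Gain in points at q = 2%:

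| Setting | T = 30 | T = 60 | T = 90 |
|---|---|---|---|
| p = 80%, events known at onset | 3.1–3.2 | 5.2 | 5.9 |
| p = 80%, events known only at the Day 8, 15 and 29 contacts | 1.6–1.7 | 4.5–4.6 | 5.4 |
| p = 80%, known at onset, s = r = 20% | 1.7 | 2.7 | 3.1 |
| p = 95%, known at onset | 0.8–0.9 | 1.5 | 1.7 |
| p = 99%, known at onset | 0.2 | 0.3 | 0.3–0.4 |

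Ranges within a cell are simulation error between runs. The contacts-only row is a lower bound, because Protocol section 8 tells women with severe events to contact the site.

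An isolated early/late pair is complete before enrolment closes in 35%, 66% and 77% of cases (T = 30, 60, 90) if known at onset, and in 16%, 53% and 68% if learned only at those contacts. When it completes with no delay, the mean undosed share is 19.5%, 26.5% and 29.0%, or about 15, 20 and 22 of 76 women.

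**The case against.** The strongest reply is that 14.1 is not an automatic rule. Its list follows a statement that all safety data are reviewed, and its items only potentially contribute to a pause. A single related severe event already fits what the Medical Monitor must flag under 10.1, so both halves of the pair should be seen. The SMC can meet on trends, and Protocol 7.1.2 has every Grade 3 diary symptom reviewed with the woman. This stands. What it leaves is that none of these routes sets a count.

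Two windows can also be defended, because first-week reactogenicity and later illness may be different signals. That is fair, but no document gives it as the reason, and the split follows the data-capture method.

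One tally would mix two severity scales. Table 10 ties Grade 3 abdominal pain to both prevented activity and medical intervention, whereas 9.2 defines severe more loosely. Amendment 1 reworded criterion 3 because unsolicited events have no numerical grade. The mismatch is real and is a cost. It does not defeat the change, since criterion 3 already applies severe to these symptoms after Day 8 and SAP 13.2 equates Grade 3 with severe.

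The rates are assumed, and late events will less often be judged related under 9.3. In the earlier open-label monovalent study of 30 adults (Protocol 2.2.3), all solicited symptoms were mild or moderate and there were no related unsolicited events. Both facts point to the low end of the tables.

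Finally, the SMC Charter and Protocol Clarification Memorandum #2 (cited in SAP section 21) were not supplied. Either may already deal with this.

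**Conclusion.** The gap exists in the supplied text and is narrow. One early, resolved case and one late case of the same related, non-serious, severe symptom meet neither two-subject criterion, and no supplied text adds the two tallies.

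A reader might infer that an automatic safeguard fails here and that such a pair would go unreviewed. The documents do not support that. The criteria sit within continuous sponsor review, and the Medical Monitor and the SMC may act without them. Nor is every symptom that crosses Day 8 lost, because SAP 13.1 re-records it.

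The illustrative gain per symptom while enrolment is open is about 1.6 to 3.2 points with 30 days of accrual, 4.6 to 5.2 with 60 and 5.4 to 5.9 with 90. It rests on an assumed 2% related severe rate with 80% early onset, and the spread reflects reporting delay. It is smaller if some cases are serious or persist past Day 8, and well under 1 point if 99% of onsets are early. This is a cheap improvement in wording, to be considered at low priority.

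**What to change.** Add one criterion to 14.1: for the nine symptoms in 9.4.1, two or more women with the same treatment-related event that is Grade 3 or higher (solicited, Table 10) or severe (unsolicited) between Day 1 and Day 29, however captured, each woman counted once. Leave the threshold, the action and the other criteria unchanged. List which reported terms match each diary symptom. Check the SMC Charter and the clarification memorandum, and align the Charter if needed.

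The cost is one sentence, a short matching list and a document check, with no new visits, data or staff. There are three downsides:

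- a slightly higher chance of a review and pause, equal to the gain above;
- the work of matching adverse event terms to diary symptoms;
- reliance on two severity scales that are similar but not identical.
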